### 7.11.3 Other Analyses

- The change from baseline in average daily time to first prodromal symptom associated with sunlight exposure between 1 hour post sunrise and 1 hour pre-sunset (Change in time to first prodromal) vs. Change from baseline in melanin density:
  - Relationship of:
    - Change in time to first prodromal versus Change from baseline in average of 6 skin segments in melanin density
    - Change in time to first prodromal versus %Change from baseline in average of 6 skin segments in melanin density
    - Change in time to first prodromal versus Change from baseline in melanin density by each skin segment
    - Change in time to first prodromal versus %Change from baseline in melanin density by each skin segment

### Plots

The relationship of primary endpoint versus melanin density will be explored graphically by providing scatter plots with loess and linear regression curves. **The matching data of change in time to first prodromal and melanin density at Week 8, 16 and 22 will be pooled into this relationship analysis.**

## 7.12 Safety Assessments

### 7.12.1 Adverse Events

The treatment emergent adverse events (TEAEs) are defined as AEs that newly occurred or increased in severity on or after the first dose of study medication.

The hepatic AEs will be selected from available TEAEs reviewed by the Clinical and Drug safety team. Then Clinical and Drug safety team will provide a list of hepatic AEs in Excel format to Data Science team. The list on Excel format will be used with clinical database to generate the hepatic AE table and listing.

The TEAEs are summarized for subjects with at least one TEAE, at least one treatment emergent adverse reaction, at least one serious TEAE, at least one serious treatment emergent adverse reaction, at least one TEAE leading to drug withdrawn, at least one treatment emergent adverse reaction leading to drug withdrawn, at least one hepatic AE, at least one Adverse Events of Special Interest (AESI) and fatal TEAE.

The frequency and incidence of TEAEs will be summarized by System Organ Class (SOC) and Preferred Term (PT) by treatment and overall. For this table, SOC is sorted by International order; then within SOC, PT is sorted by descending counts under MT-7117

Total group, then descending counts under Placebo group, then alphabetic order for PTs with the same count.

The AE summaries will be presented for the following:

- TEAEs by SOC and PT
- TEAEs by SOC, PT and severity
- TEAEs by SOC, PT and relationship
- Treatment emergent adverse reactions by SOC and PT
- Treatment emergent adverse reactions by SOC, PT and severity
- Serious TEAEs by SOC and PT
- Serious treatment emergent adverse reactions by SOC and PT
- TEAEs leading to drug withdrawn by SOC and PT
- TEAEs by SOC and PT for TEAEs with frequency  $\geq 3\%$  in total MT-7117 group
- Treatment Emergent Hepatic AEs by SOC and PT

For each of the summaries will be done at the subject level - multiple occurrences of the same event within a subject will be counted once in the summaries by SOC and PT; multiple occurrences of the same event within a subject will be counted once in the maximum intensity category (severe > moderate > mild) and/or maximum drug relationship category (reasonable possibility, no reasonable possibility). If intensity or relationship is found to be missing the most severe occurrence will be imputed for that particular summary.

All AEs for each subject, including multiple occurrences of the same event, will be listed.

Deaths that occur during the study will be listed in a data listing. The data listings for serious TEAE and TEAE leading to drug withdrawn will be generated as well.

### 7.12.2 Laboratory Tests

Lab test values and changes from baseline will be summarized descriptively by treatment and visit.

The lab tables will be generated for each Lab categories (Hematology, Coagulation, Biochemistry and Urinalysis).

All laboratory data will be listed with clinically relevant values flagged (L=Lower than lower limit of normal range, H=Higher than upper limit of normal range or A=Abnormal).

The number and percentage of subjects with lab values out of normal range for each lab test will be summarized in table by treatment. The percentage will be based on the number of subjects of safety population in the corresponding group.

In addition, following clinical relevant ranges (and flags) will also be considered for summary table. The count and percent of subjects meeting the criteria will be presented. The percentage will be based on the number of subjects of safety population in the corresponding group.

- ALT and/or AST  $\geq 3 \times$  Upper Limit of Normal Range (ULN), 4xULN, 6xULN, 10xULN
- AST and/or ALT  $\geq 3 \times$  ULN with Total bilirubin  $\geq 2 \times$  ULN
- Total bilirubin  $\geq 2 \times$  ULN

- Creatinine  $\geq 2 \times$  ULN
- ALP  $\geq 3 \times$  ULN
- Hy's Law (ALT or AST  $> 3 \times$  ULN and TBL  $> 2 \times$  ULN and Alkaline phosphatase  $< 2 \times$  ULN)

The figure of mean (or median) and standard error value of ALT, AST, Total bilirubin and Alkaline phosphatase by visit will be plotted.

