3.2 Rationale for Study Design and Treatment Regimens

The objectives of this study are to obtain efficacy, tolerability, and safety data for the selected two doses (██████ and ██████ day) of MT-7117 and placebo when administered to subjects with EPP over a 16-week treatment period. A standard randomized, placebo controlled, double-blind treatment allocation is considered appropriate in order to obtain unbiased results in this study. Safety and PK/pharmacodynamic effects will be evaluated based upon these comparable data from the Phase I, MT-7117-E01 study.

Abnormal biochemical parameters related to the hepatic function were observed in rats and monkeys. In MT-7117-E01 human study, in subjects receiving 14 days of study drug, treatment emergent transaminase elevations were reported in 6/36 (17%) subjects receiving MT-7117 and 2/12 (17%) subjects receiving placebo. Of the six subjects receiving MT-7117 for 14 days reporting treatment emergent transaminase elevations, 4 had elevated baseline transaminase values. Therefore, frequent assessments of liver function markers are performed in this study.

The 16-week treatment period is considered a sufficient duration for evaluation of the efficacy and tolerability of MT-7117 for this study. Subjects will attend a follow-up visit 6 weeks after the end of treatment (or early termination) which is considered a sufficient duration to evaluate pigmentation recovery and safety of subjects. For the primary and secondary endpoints, the effect of MT-7117 on the duration of sunlight exposure will be measured using a sunlight exposure diary. Melanin density assessments are safe and routinely used in clinical studies of skin disorders and will be used in this study to assess the effect of MT-7117 on pigmentation. The effect of MT-7117 on quality of life will be assessed using questionnaires. The exit interview questionnaire will measure the clinical

Mitsubishi Tanabe Pharma Development America, Inc.

benefit of MT-7117 and perspectives of quality of life.

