4.4 Exclusion Criteria

A subject will NOT be eligible for this study if ANY of the following criteria apply:

1. History or presence of photodermatoses other than EPP.
2. Subjects who are unwilling or unable to go outside during daylight hours (e.g., between 1 hour post sunrise and 1 hour pre-sunset) during the study.
3. Presence of clinically significant hepatobiliary disease based on LFT values at Screening.
4. Subjects with AST, ALT, ALP $\geq 3.0 \times$ upper limit of normal (ULN) or total bilirubin $> 1.5 \times$ ULN at Screening.
5. Subjects with or having a history (in the last 2 years) of excessive alcohol intake in the opinion of the Investigator.
6. History or presence of melanoma and/or atypical nevus at Screening.
7. History of familial melanoma (defined as having 2 or more first-degree relatives, such as parents, sibling and/or child).
8. History or presence of pre-malignant skin lesion, squamous cell carcinoma, basal cell carcinoma, or other malignant skin lesions.

9. History or presence of psychiatric disease judged to be clinically significant by the Investigator and which may interfere with the study evaluation and/or safety of the subjects.
10. Presence of clinically significant acute or chronic renal disease based upon the subject's medical records including hemodialysis; and a serum creatinine level of greater than 1.2 mg/dL or a glomerular filtration rate (GFR) <60 ml/min.
11. Presence of any clinically significant disease or laboratory abnormality which, in the opinion of the Investigator, can interfere with the study objectives and/or safety of the subjects.
12. Pregnancy or lactation.
13. Females of child-bearing potential and male subjects with partners of child-bearing potential unwilling to use adequate contraception measures as described in the protocol.
14. Treatment with phototherapy within 3 months before Randomization (Visit 2).
15. Treatment with afamelanotide within 3 months before Randomization (Visit 2).
16. Treatment with cimetidine within 4 weeks before Randomization (Visit 2).
17. Treatment with antioxidant agents at doses which, in the opinion of the Investigator, may affect study endpoints (including but not limited to beta-carotene, cysteine, pyridoxine) within 4 weeks before Randomization (Visit 2).

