10.2.3 Safety Assessments

Adverse Events

AEs are considered as treatment-emergent if they occur after the first dose administration of study drug or if a pre-dose event increases in severity following dosing.

AEs will be assumed to be treatment-emergent, unless there is clear evidence (if necessary through comparison of partial dates) to suggest that the AE started prior to the first dose of IMP.

The frequency and incidence of treatment-emergent AEs (TEAEs) will be summarized by system organ class (SOC) and preferred term (PT) by treatment period and overall. Summaries will also be produced by relationship to study drug and by maximum severity. The summary will be sorted by International Agreed Order for SOC and alphabetical order for preferred term (or by frequency from the highest to the lowest).

The following summaries will be presented:

- Summary of TEAEs by SOC and PT.
- Summary of TEAEs by SOC, PT and severity.
- Summary of TEAEs by SOC, PT and relationship.
- Summary of Serious TEAE by SOC and PT.
- Summary of TEAE leading to drug withdrawn by SOC, PT.

For each of the summaries produced at the subject level, multiple occurrences of the same event within a subject will be counted once in the summaries by SOC and preferred term; multiple occurrences of the same event within a subject will be counted once in the maximum severity category (severe > moderate > mild) and/or maximum study drug

relationship category (reasonable possibility/no reasonable possibility). If severity or relationship is found to be missing, the most severe occurrence will be imputed for that particular summary.

Safety laboratory tests

Routine laboratory safety tests include hematology, coagulation, biochemistry and urinalysis.

Continuous laboratory parameters will be summarised by scheduled time point and treatment group. Observed values as well as changes from baseline (Day -1) will be summarized by treatment groups. Categorical parameters will be summarized by frequency counts and percentages of subjects within each category.

The laboratory data will be listed in full with clinically relevant values flagged (L=Lower than normal range, H=Higher than normal range or A=Abnormal if no reference range).

The number of subjects with post baseline assessments \geq x3 ULN and \geq x5 ULN and so on will be calculated for ALT, AST, GGT, ALP, direct and total bilirubin and summarized by treatment for each post baseline visit.

Vital signs and electrocardiogram data

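### SAP 7.12.2 counts abnormal liver tests without reference to baseline, although subjects may enter with AST, ALT or ALP up to just under 3×ULN

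*SAP*

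**What the plan says.** **Entry.** Protocol 4.4, exclusion 4, bars AST, ALT or ALP at 3.0×ULN or above and total bilirubin above 1.5×ULN, judged at Screening. Exclusion 3 bars "Presence of clinically significant hepatobiliary disease based on LFT values at Screening". A raised enzyme below 3×ULN that is not judged clinically significant is admissible.

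**SAP counts.** SAP 7.12.2 plans two sets of laboratory counts.
- Out of range: "The number and percentage of subjects with lab values out of normal range for each lab test will be summarized in table by treatment".
- ULN multiples: ALT and/or AST at 3, 4, 6 and 10×ULN, ALP at 3×ULN, total bilirubin at 2×ULN, and combinations. For these, "The count and percent of subjects meeting the criteria will be presented".
- Denominator in both: "The percentage will be based on the number of subjects of safety population in the corresponding group".

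Neither set mentions post-baseline timing, baseline status or worsening. The section also plans descriptive values and changes from baseline by treatment and visit, a full flagged listing, and by-visit figures for four liver markers. It plans no shift table.

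**Protocol counterpart.** Protocol 10.2.3 describes "The number of subjects with post baseline assessments" at or above given ULN multiples, by treatment for each post-baseline visit. SAP section 8 states that the protocol's analyses are unchanged.

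**ECG contrast.** SAP 7.12.4 conditions its QTc categories on a baseline below 450 msec and plans shift tables from baseline to end of treatment.

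**The concern.** Liver markers are the main monitored laboratory risk: Protocol 3.3 says MT-7117 may raise them and has them measured at every planned visit. A reader of the liver tables wants to know how many subjects became abnormal, or got worse, after dosing. The SAP counts give how many were ever abnormal, whatever their starting point.

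The protocol's own Phase I account shows that this is a realistic problem. Of the six MT-7117 subjects "reporting treatment emergent transaminase elevations, 4 had elevated baseline transaminase values". With 34 subjects per arm, a handful who arrive with raised enzymes can move an arm's out-of-range percentage noticeably, and the planned counts would not show that this was the reason.

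**Working it through.** **1. Reproduce the documents' figure.** Protocol 3.2 gives transaminase elevations of 6/36 = 16.7% on MT-7117 and 2/12 = 16.7% on placebo; both round to the stated 17%. Leaving out the four MT-7117 cases with raised baseline gives (6 − 4)/36 = 5.6%, or 2/32 = 6.3% if those four also leave the denominator. The placebo figure cannot be recomputed, because baseline status is not given for its two cases (range 0/12 to 2/12).

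**2. Chance of being counted with no drug effect.** Document input: 7 scheduled post-dose liver samples (Visits 3 to 9). Assumptions: a subject's values vary log-normally and independently around a usual level m (in ×ULN), with within-subject CV of 10% to 30%.

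s = √ln(1 + CV²); p = P(Z > ln(T/m)/s) for threshold T; P(at least one of 7) = 1 − (1 − p)⁷.

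Example: m = 2.5, T = 3, CV 20%. Then s = 0.198, ln(3/2.5)/s = 0.92, p = 0.179, and 1 − 0.821⁷ = 75%.

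| Usual level (×ULN) | Any value ≥3×ULN: CV 10% | CV 20% | CV 30% |
|---|---|---|---|
| 1.2 | 0% | 0% | 0.6% |
| 1.5 | 0% | 0.2% | 6% |
| 2.0 | 0% | 13% | 46% |
| 2.5 | 21% | 75% | 89% |
| 2.9 | 96% | 98% | 99% |

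For the out-of-range count (T = 1), any usual level of 1.2×ULN or more gives a probability of essentially 100% at all three CVs. So almost every subject with a raised usual level enters the out-of-range table, while the ≥3×ULN rows are touched mainly by subjects at about 2×ULN or higher.

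**3. Unequal rises count alike.** From 2.9×ULN, reaching 3×ULN takes 3/2.9 − 1 = 3.4%. From 1.0×ULN it takes 3/1 − 1 = 200%.

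**4. Chance imbalance at 34 per arm.** Assumed share entering abnormal: b = 4/36 = 11% (the least that the Phase I MT-7117 group can have had) up to 25% (assumed).
- Expected per arm: 34 × 0.111 = 3.8; 34 × 0.25 = 8.5.
- SD of the difference between two arms, √(2b(1 − b)/34): 7.6 and 10.5 percentage points.
- Probability that two arms differ by four or more such subjects (4/34 = 11.8 points), exact binomial: 17% and 33%.

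**5. Dilution of the out-of-range contrast.** Assume new-onset rates of 5% on placebo and 20% on active among subjects normal at entry, and that everyone abnormal at entry is counted. The observed rate is b + (1 − b) × new-onset rate.
- b = 0: 5.0% v 20.0%, ratio 4.0, difference 15.0 points.
- b = 11%: 15.6% v 28.9%, ratio 1.86, difference 13.3 points.
- b = 25%: 28.7% v 40.0%, ratio 1.39, difference 11.3 points.

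**6. Day 1 values.** Visit 2 laboratory samples are taken on the day of first dose (Protocol 5.3.2.1), after the Screening judgement. Protocol 10.2.3 keeps pre-dose results out of the threshold counts; SAP 7.12.2, read literally, does not.

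**The case against.** The strongest reply has five parts.

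- **The 3×ULN rows do not count abnormality of that degree carried in from Screening.** Values at or above 3×ULN at Screening are excluded, so anyone counted there crossed the line afterwards. The bilirubin row at 2×ULN is likewise above its entry ceiling of 1.5×ULN. This stands. It leaves only the narrower issues of small rises from just under the line and of Day 1 values.
- **The counts are not labelled treatment-emergent.** This stands. A reader might infer that the SAP presents pre-existing abnormality as drug-induced; the text does not say so. The fault is that the two are not separated.
- **Baseline is not ignored throughout.** Changes from baseline, listings and by-visit figures are planned, and SAP 7.12.1 tabulates hepatic events drawn from events that are new or worsened after first dose. This stands in part. Group summaries of change do not show which subjects crossed a limit from a raised start. Listings do, but only by hand and without a stated rule.
- **Absolute ULN multiples match the protocol's hepatic criteria in 4.5 and 8.3.** This stands, and it is why the all-subject counts should stay.
- **The missing post-baseline wording is an omission that the protocol cures.** Probably so, but the tables will be programmed from the SAP, and its section 8 gives no sign that the difference was noticed.

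The high crossing probabilities also need a usual level of 2.5×ULN or more, and the documents do not say how many subjects, if any, are near it.

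**Conclusion.** The point holds in a limited form. As written, the out-of-range table combines abnormality present at entry with abnormality that appears later, and no planned laboratory count or table separates them subject by subject. The rows at 3×ULN and above are affected only at the margin.

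A reader might go further and infer bias against MT-7117. The documents do not support that. Randomisation balances baseline abnormality in expectation, and the Phase I rates were equal at 17% in both groups. What follows is inflated counts in every arm, a diluted contrast and exposure to chance imbalance.

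The sizes (17% to 33% for a gap of four or more subjects; a ratio of 4.0 shrinking to between 1.86 and 1.39) rest on an assumed 11% to 25% entering abnormal and on assumed new-onset rates. The crossing probabilities are illustrative and depend on the assumed CV and usual level. That the counts make no reference to baseline depends on none of these assumptions. In an exploratory Phase 2 study this is a modest reporting gap, worth closing because the affected tables concern the main monitored risk.

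**What to change.** In SAP 7.12.2:

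1. Restrict the out-of-range and threshold counts to post-baseline values, as Protocol 10.2.3 already does for the threshold counts, and state whether unscheduled results count.
2. For ALT, AST, ALP and bilirubin, present the out-of-range and threshold counts by baseline at or below ULN versus above ULN, and/or add a shift table by arm from baseline (last pre-dose value, as in SAP 5.4.2) to worst post-baseline value.
3. Keep the all-subject post-baseline counts alongside.

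Excluding subjects who already met a given limit at baseline would not be enough: someone at 2.9×ULN has not met 3×ULN and would still be counted after a trivial rise. The split or the shift table is what shows this.

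The cost is SAP wording and a few extra rows from data already collected. Cells for subjects above ULN at baseline will be small. No eligibility, monitoring or withdrawal rule changes.

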4.5 Withdrawal of Individual Subjects

A subject will be withdrawn from study if ANY of the following criteria are met:

1. The subject requests to voluntarily withdraw from further participation in study.
2. The subject is significantly noncompliant with the protocol.
3. Continuing in the study would be detrimental to the subject's safety in the opinion of the Investigator, e.g.,
 - a. The subject experiences intolerable AEs or SAEs.
 - b. The subject has clinically significant changes in safety parameters at any of the post-dose time points, as confirmed with a repeat assessment performed as soon as possible after the initial out-of-range result.
 - c. If there are any clinically significant adverse findings from post-baseline nevi evaluation, subjects will not be allowed to continue taking study medication (see Section 6.9.4). If biopsy findings are benign, subject may reinitiate study treatment based on investigators discretion.
 - d. Development of any clinically significant liver dysfunction, as follows:
 - i. ALT or AST $>6 \times$ ULN.
 - ii. ALT or AST $>4 \times$ ULN for more than 2 weeks.
 - a) Elevated total bilirubin $>2 \times$ ULN and ALT or AST $>2 \times$ ULN or
 - b) Symptoms consistent with liver dysfunction (e.g., fatigue, nausea, vomiting, abdominal pain or tenderness, fever, rash, eosinophilia $>5\%$) with concomitant ALT or AST values $>3 \times$ ULN.

Subjects (meeting above criteria) do not require withdrawal if alternative etiology is identified on discussion with the Study Medical Monitor.

Subjects meeting above criteria (with or without alternative etiology) should be reported as hepatic AE of special interest (AESI) (see Section 8.3).

These subjects will be discontinued from treatment but may be managed on study per the Investigator's discretion and followed per protocol (see Section 8.6). In addition, a subject may be withdrawn from treatment at any time for reason(s) other than those listed here.

If a subject is discontinued prematurely from the treatment or the study, the date the subject is withdrawn and the reason for withdrawal will be recorded on the site source documents and in the electronic Case Report Form (eCRF). Subjects who withdraw or are withdrawn from study treatment should be encouraged to complete all study visits and study procedures as outlined in the protocol.

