8.3 Adverse Events of Special Interest

One AESI that will be considered during this study includes hepatic AESIs, defined as

- Clinically significant liver dysfunction, as follows:
 - ALT or AST >6 x ULN.
 - ALT or AST >4 x ULN for more than 2 weeks.
 - Elevated total bilirubin >2 x ULN and ALT or AST >2 x ULN, or
 - Symptoms consistent with liver dysfunction (e.g., fatigue, nausea, vomiting, abdominal pain or tenderness, fever, rash, eosinophilia >5%) with concomitant ALT or AST values >3 x ULN.
- Hepatic AEs or hepatic laboratory abnormalities that lead to study medication interruption or discontinuation (see Section 4.5).

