#### **2.4.4 Clinical laboratory examinations**

The lab tests are conducted for the following lab categories

- Hematology
- Coagulation
- Biochemistry
- Urinalysis

The liver function markers (ALT, AST, GGT, ALP, direct and total bilirubin) will be collected.

The lab test names are listed in the table below.

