## 8. CHANGES FROM THE PROTOCOL

There are no changes to the statistical analyses that are described in the protocol.

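### The SAP liver table omits 9 of the 12 threshold counts named in the protocol and has no row for the bilirubin AESI criterion, yet SAP section 8 declares no changes

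*SAP*

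**What the plan says.** Protocol 10.2.3 (Safety Assessments) names two thresholds, at least 3x and at least 5x ULN. It says that subject counts at these levels "and so on will be calculated for ALT, AST, GGT, ALP, direct and total bilirubin and summarized by treatment for each post baseline visit".

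Protocol 8.3 defines the hepatic AESI. One of its criteria is "Elevated total bilirubin >2 x ULN and ALT or AST >2 x ULN, or" the symptom-based alternative that follows it. Protocol 4.5 has the same combination among its liver criteria and adds: "Subjects meeting above criteria (with or without alternative etiology) should be reported as hepatic AE of special interest (AESI").

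SAP 2.4.4 keeps all six markers: "The liver function markers (ALT, AST, GGT, ALP, direct and total bilirubin) will be collected". SAP 7.12.2 then introduces its threshold list with "following clinical relevant ranges (and flags) will also be considered for summary table". The liver rows are:
- ALT and/or AST at 3x and above ("ULN), 4xULN, 6xULN, 10xULN")
- AST and/or ALT at 3x or more "ULN with Total bilirubin" at 2x or more
- total bilirubin at 2x or more
- ALP at 3x or more
- a Hy's Law row requiring ALT or AST above 3x, total bilirubin above 2x and ALP below 2x

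SAP section 8 reads: "There are no changes to the statistical analyses that are described in the protocol".

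**The concern.** The liver is the only organ for which the protocol defines an AESI. Protocol 3.2 explains why: hepatic biochemistry was abnormal in rats and monkeys, and frequent liver assessments were planned for that reason. The introduction also notes liver manifestations in about 3% of patients with EPP. GGT and direct bilirubin are drawn even at the liver-only Week 1 and Week 2 collections.

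If the SAP is programmed as written, the report will lack safety counts that the protocol committed to. It will also have no laboratory-derived count against which the reported bilirubin-based AESIs can be checked. A reader who relies on section 8 would not know that anything differs.

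**Working it through.** No power or alpha calculation is involved. The check sets the two lists side by side and then tests the criteria on cases.

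**1. Threshold counts.** The protocol names 6 analytes x 2 thresholds = 12 counts.

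| Analyte | 3x in SAP list? | 5x in SAP list? |
|---|---|---|
| ALT | yes (merged with AST) | no (4x, 6x, 10x) |
| AST | yes (merged with ALT) | no (4x, 6x, 10x) |
| ALP | yes | no |
| Total bilirubin | no (2x only) | no |
| GGT | no | no |
| Direct bilirubin | no | no |

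Three are covered and 12 - 3 = 9 are absent. The protocol asks for the counts at each post-baseline visit. The SAP does not say that its threshold counts are by visit. The protocol's wording leaves room for further thresholds, but it states 3x, 5x and all six analytes outright, so its openness does not remove any of them.

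**2. The bilirubin AESI criterion.** Values are multiples of ULN, with ALP at 1x.

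| ALT or AST | Total bilirubin | Protocol criterion (both >2x) | SAP combined row (≥3x with ≥2x) | SAP Hy's Law row | SAP bilirubin ≥2x row |
|---|---|---|---|---|---|
| 1.0 | 2.5 | no | no | no | yes |
| 2.1 | 2.5 | yes | no | no | yes |
| 2.6 | 2.3 | yes | no | no | yes |
| 2.9 | 2.5 | yes | no | no | yes |
| 3.0 | 2.0 | no | yes | no | yes |
| 3.1 | 2.5 | yes | yes | yes | yes |

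Any subject with ALT/AST above 2x and below 3x, and bilirubin above 2x, meets the protocol criterion but falls in neither combined row. In the threshold table that subject appears only under total bilirubin at 2x or more, together with subjects whose transaminases are normal (first line). Subtracting the combined row from the bilirubin row does not separate the two kinds of subject. The 3.0/2.0 line shows a smaller mismatch in the other direction: the SAP combined row uses at-least where the protocol uses greater-than.

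This zone can be reached. Exclusion 4 in Protocol 4.4 admits AST and ALT below 3x and total bilirubin up to 1.5x. A subject who enters at ALT 2.5x and whose bilirubin later exceeds 2x meets the criterion with no change in ALT.

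**3. Section 8 against the rest of the SAP.** Two further departures are not recorded there:
- *Non-parametric analysis.* Protocol 10.2.2.1 applies the Wilcoxon and Hodges-Lehmann analysis to change in symptom-free exposure duration, in hours. SAP 7.11.1 applies it to change in time to first prodromal symptom, in minutes, and adds multiple imputation.
- *Count models.* Protocol 10.2.2.2 gives treatment and a baseline count. SAP 7.11.2 adds the 30-minute stratum.

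**The case against.** The strongest reply is that little is lost from the report. Protocol 4.5 requires subjects meeting the liver criteria to be reported as hepatic AESIs. SAP 7.12.1 counts subjects with at least one AESI and at least one hepatic AE, and tabulates the hepatic events. GGT and direct bilirubin keep descriptive statistics by treatment and visit, including the maximum, as well as out-of-range counts and full listings. ALP at 3x and total bilirubin at 2x have rows, and both are plotted. The SAP's 4x and 6x transaminase cuts match AESI cut-points and bracket the missing 5x.

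Most of this stands, and it rules out some stronger readings:
- *A reader might infer that AESI cases go uncounted.* They do not, if sites report them. But the AESI row pools all criteria, and the hepatic list is selected from reported events, so neither is a laboratory-derived check.
- *A reader might infer that GGT and direct bilirubin appear only as out of range, or that a cholestatic excess above 3x would be invisible.* The descriptive tables, the ALP row and the bilirubin row contradict this. What is missing is the number of subjects by multiple of ULN for GGT and direct bilirubin. A maximum per arm does not give that number. The by-visit tables also leave out unscheduled visits and retests (SAP 5.4.4), and Protocol 5.3.5 classes repeat liver tests as unscheduled.
- *A reader might infer that the removal of PGIC_2 and the exit interview was concealed.* SAP 2.11 discloses it with a reason, SAP 7.12.7 plans listings, and Protocol 10.2.2.2 specified no analysis for either. Only a cross-reference is missing.

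It is also fair to say that the SAP may refine the protocol, and that its Wilcoxon variable fits the primary endpoint better. That is a reason to record the change in section 8. It does not support a statement that there was none.

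**Conclusion.** The point holds as a mismatch between protocol and SAP that should be corrected. Nine of 12 named threshold counts and the by-visit presentation are missing, no laboratory row isolates the bilirubin AESI criterion, and the section 8 statement is inaccurate on the liver table and on two efficacy analyses. Primary inference and the monitoring of subjects are not affected.

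The number of subjects involved cannot be predicted from the documents. If all 34 planned subjects per arm are in the safety population, each one changes a row by 1/34 = 2.9 percentage points. That is the size of a misplacement in one table; it does not mean the subject is lost from the report. The conclusion assumes that the SAP list is complete as written and that the outputs follow it.

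**What to change.** 1. In SAP 7.12.2, add subject counts at 3x or more and 5x or more ULN for all six analytes named in Protocol 10.2.3, by treatment and post-baseline visit. Keep the existing SAP rows.
2. Add a row for total bilirubin above 2x with ALT or AST above 2x ULN, in the wording of Protocol 8.3. Add no condition that the protocol does not state, such as both values coming from the same draw; otherwise the row would not match the definition it is meant to count.
3. Replace the section 8 sentence with a list of the actual departures: the liver thresholds (if not restored), the Wilcoxon/Hodges-Lehmann variable and its imputation, the stratum in the count models, and a cross-reference to SAP 2.11.

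The cost is a few table rows from laboratory data already collected and one rewritten SAP paragraph. No new assessment is needed, and no clinical rule changes.
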